**16) Sharing of results with subjects**

Participants may follow up with the research staff upon completion of the study to learn about study results.

**See HSPP website for submission requirements.**

**Items needed for approval:**

- **F107: Verification of Training Form**
- **Current PI/Co-PI CVs or biosketch**, if not included with copy of grant application
- **Informed Consent/Permission/Assent Form(s)** – including study specific release of information documents, DHHS approved sample consent forms. If consent will not be documented in writing, a script of information to be provided orally to subjects

**Other Items as applicable:**

- **Appendix A - Children**
- **Appendix B - Drug/Device**
- **Appendix C- Multi Site Research**
- **Appendix D- Pregnant Women and Neonates**
- **Appendix E- Prisoners**
- **Appendix F- Waiver of Consent/ PHI**
- **Biosafety Review letter** (for UA - Institutional Biosafety Committee)
- **Certificate of Confidentiality**
- **Compressed Gases Review letter** (for UA – Research Instrumentation)
- **Contract** – complete or draft copy of contract including budget
- **Data Collection Tools** – surveys, questionnaires, diaries not included in the protocol, data abstraction form for records review
- **Data Monitoring Charter and Plan**

- **Drug/Device information** – Investigator's Brochure, drug product sheet, device manual, user's manual, instructions for use, package insert, IND/IDE documentation, FDA 1572 form, 510k indication, FDA exemption, sponsor determination of device risk, etc.
- **Export Control Review**
- **Grant Application(s)** – cover-to-cover copy of grant, regardless of home institution or funding agency, and a copy of the Notice of Grant Award.
- **Other Approval letters** (e.g., school districts, Tribal, other IRB approvals)
- **Participant Materials** – written materials to be provided to or meant to be seen or heard by subjects (e.g. study newsletter, physician to participant letter, wallet cards, incentive items, holiday/birthday cards, certificates, instructional videos/written guides, calendars, certification of achievement, etc.)
- **Payer coverage analysis**
- **PHI Authorization Form(s)**
- **Protocol** – including all amendments/revisions, sub- or extension-studies
- **Radiation Safety Review** letter- needed regardless if the radiation device is approved and used standard of care
- **Recruitment Materials** – telephone scripts, flyers, brochures, websites, email texts, radio/television spots, newspaper advertisements, press releases, etc.
- **Scientific Review Committee** letter (for cancer related projects – AZCC SRC; other units as applicable if the unit has a scientific review committee)
- **Site Authorizations** for research purposes and/or access to administrative records/samples
  - External sites (such as schools, other hospitals or campuses, etc.)
  - B-UMG approval
- **Supplemental site information** (for sites engaged in research where the UA is the IRB of record)
  - Copy of any approvals granted from that site (including determinations if this site has an IRB of its own)
  - Site-specific F107
  - Copy of the site's human subjects training policy
  - CV and medical license (if applicable) of site PI
- **Travel Authorization documentation** (for UA – Office of Global Initiatives)
- **Use of retrospective research samples and/or data** – IRB approval letter, original consent under which samples/data were collected, letter allowing access to samples

Effects of Two Psychosocial Wellness Workshops on Sleep, Stress Management and Wellbeing: Exploration of Psychophysiological Mechanisms

Brief title: Student Wellness Workshop study (SWW)

NTC number: not yet assigned

Date of document: 12/15/2017

Statistical analysis will be conducted in IBM SPSS 24.0 using Linear Mixed Models and selective post-hoc comparisons focusing on within-group change for YESplus and WOW at post and follow-up compared to pre-workshop. For each model, results will be reported for main effects of Visit (pre, post, follow-up) and Group (YESplus, WOW), as well as Visit x Group interaction. However, due to limited statistical power of this sample to detect interactions, analysis will focus on within-group change from pre- to post-workshop, as well as pre to follow-up, and corresponding within-group effect size. Thus, to balance type I and type II error with these within-group comparisons, a Bonferroni correction will be applied by multiplying uncorrected p values by 4 (the number of post-hoc comparisons per model), allowing alpha to remain at .05 for significance. Effect size estimates will be calculated with Cohen's d.

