**Questionnaires.** Participants will be asked to complete a custom survey inquiring about information such as GPA and self-rated stress of specific situations, as well as the Morningness-Eveningness Questionnaire (MEQ) with an online format at T1. In addition, participants will be asked to complete a custom survey inquiring about information such as current stress-management techniques, the short-form Mood and Anxiety Symptom Questionnaire (MASQ), Perceived Stress Scale (PSS), Pittsburgh Sleep Quality Index (PSQI), Big Five personality inventory (Big-5), Rosenberg Self-Esteem Scale (RSES), Satisfaction With Life Scale (SWLS), and Social Connectedness (SC) measures online for all three time points. During each laboratory visit, participants will also be asked to complete the state-specific items of the State-Trait Anxiety Inventory (STAI).

**Electrocardiogram (ECG) measures.** Individual electrodes will be placed at collarbone and lower ribcage locations to collect ECG recordings. Participants will be instructed to sit quietly for 2 minutes for each of the four resting recordings (baseline, post-stress, 30-min-post, 45-min-post). ECG data will then be processed to determine measures including resting heart rate (HR), heart rate variability (HRV), and

respiratory sinus arrhythmia (RSA). Supplementary HR data will be collected via pulse oximetry, a device consisting of a soft clip placed around the participant's pointer finger. To control for respiration that may influence HR data, respiratory inductance plethysmography will be recorded concurrently via two adjustable belts placed around the participant's abdomen, one passing around the sternum and the other passing around the navel. As an additional covariate of Body Mass Index (BMI) for ECG analysis, height and weight will also be measured at each laboratory visit.

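### The SAP leaves the T1 mean free in each arm, so its Group main effect mixes in a pre-workshop visit and its Visit x Group test is valid but less precise than a T1-adjusted comparison.

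*SAP*

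**What the plan says.** The SAP is one paragraph. It specifies linear mixed models in which "results will be reported for main effects of Visit (pre, post, follow-up) and Group (YESplus, WOW), as well as Visit x Group interaction". It then explains its emphasis: "due to limited statistical power of this sample to detect interactions, analysis will focus on within-group change". No power figure, effect size, visit correlation or covariance structure is given, and nothing says that T1 is a covariate or that the arms share a T1 mean.

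The protocol has no analysis section. In Section 3, item 8 (Measures), the only covariate it names is body mass index: "As an additional covariate of Body Mass Index (BMI) for ECG analysis". Respiration is also recorded as a control for the heart-rate data. Item 8 also states that participants are randomised, that T1 comes before the workshop, and that T2 and T3 come after it. Item 6 plans 100 students and shows no calculation behind that number.

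**The concern.** Assignment is random, so T1 differences between arms should be chance. A model that gives each arm its own T1 mean ignores this, with two consequences.

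First, the Group main effect averages three visits, one of which cannot show a workshop effect. A reader who takes this line of the output as the YES+ versus WOW! result sees a shrunken effect with T1 noise added.

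Second, the between-arm question is left to an interaction test on unadjusted changes, which uses the T1 data less efficiently than it could. This matters because WOW! was included to control for expectancy, time, group contact and shared content (protocol Section 3, items 2 and 8). Only a between-arm comparison uses that control. The SAP moves its focus away from that comparison on grounds of power, while its own model form gives some of that power away.

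**Working it through.** There is no stated power calculation to reproduce.

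**From the documents:** three visits, with T1 before the workshop; two randomised arms; 100 students; alpha 0.05. **Assumed, because the documents are silent:** 1:1 allocation (n = 50 per arm), two-sided tests, SD 1 at every visit, equal correlation rho between visits, the same true difference d at T2 and T3, no dropout and no clustering.

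**Step 1: what the Group main effect estimates.** With equal weight on the three visits, the expected difference is (0 + d + d)/3 = 2d/3. An observed T1 difference enters directly with weight one third. This step needs no value for rho. The per-person variance of the three-visit mean is (1 + 2rho)/3. At d = 0.5 and rho = 0.5 the effect is 0.333, the standard error is sqrt(0.667 x 2/50) = 0.163, and power is 0.52.

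**Step 2: variance with and without T1 adjustment.**
- T2 alone: change score 2(1 - rho); adjusted 1 - rho^2; ratio (1 + rho)/2, which is 0.75 at rho 0.5.
- Average of T2 and T3: change from T1, 1.5(1 - rho); adjusted (1 + rho)/2 - rho^2; ratio (1 + 2rho)/3. At rho 0.5 this is 0.50/0.75 = 0.67.

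Both ratios are below 1 for every rho below 1.

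**Step 3: the 2-df test.** With equal effects at T2 and T3, the noncentrality is (n/2)d^2 divided by the average-of-T2-and-T3 variance in step 2. At d = 0.5 and rho = 0.5:
- unadjusted: 25 x 0.25/0.75 = 8.33
- adjusted: 25 x 0.25/0.50 = 12.5

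With F on 2 and 196 df these give power 0.73 and 0.89.

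**Step 4: power, unadjusted to T1-adjusted** (noncentral F for 2 df, noncentral t for 1 df):

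| n per arm, d, rho | 2-df test | T2 and T3 average | T2 alone | Three-visit Group effect |
|---|---|---|---|---|
| 50, 0.5, 0.3 | 0.57 to 0.85 | 0.68 to 0.91 | 0.55 to 0.74 | 0.62 |
| 50, 0.5, 0.5 | 0.73 to 0.89 | 0.82 to 0.94 | 0.70 to 0.82 | 0.52 |
| 50, 0.5, 0.7 | 0.92 to 0.97 | 0.96 to 0.98 | 0.89 to 0.93 | 0.45 |
| 50, 0.5, 0.8 | 0.987 to 0.995 | 0.995 to 0.998 | 0.97 to 0.98 | 0.43 |
| 50, 0.3, 0.5 | 0.32 to 0.45 | 0.40 to 0.56 | 0.32 to 0.40 | 0.23 |
| 40, 0.5, 0.5 | 0.62 to 0.81 | 0.72 to 0.88 | 0.60 to 0.72 | 0.44 |

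A simulation of 4,000 trials at d = 0.5 and rho 0.3, 0.5 and 0.7 agreed to within about 2 points. It covered the T2 contrasts, the Group main effect and the adjusted average.

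**The case against.** The SAP never calls the Group main effect a treatment effect. It is a routine model term, and the interaction is the proper test of differential change. That is correct: the interaction test is valid and unbiased, and nothing here makes it wrong. But the SAP undertakes to report the Group term for every model, and nothing warns the reader that it is diluted.

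A reader might infer that the limited power is mainly a product of the model. The documents do not support this. They give no effect size, and WOW! is an active comparator that shares much with YES+, so small differences are plausible. At 0.3 SD and rho 0.5 even the adjusted average reaches only 0.56.

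A reader might also set the 2-df interaction (0.73) against the adjusted 1-df average (0.94) and credit the whole gain to adjustment. Of those 21 points, 9 come from replacing 2 df with 1 df (0.73 to 0.82), and they rely on equal effects at T2 and T3. Adjustment supplies the other 12.

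Three further limits stand:
- The documents give no rho. The outcomes include personality, self-esteem and life-satisfaction scales, for which high correlations cannot be excluded, and the gain is then small.
- Fifty per arm is assumed, and the SAP does not give the size of its sample.
- Affiliated students are allocated together and workshops are run in groups. Clustering would lower every power shown, and no intraclass correlation is available.

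**Conclusion.** The point holds in two parts of different strength. That the three-visit Group main effect does not estimate a treatment effect (2d/3 plus chance T1 imbalance) follows from the stated model and needs no assumed correlation. That the interaction test is less efficient than a T1-adjusted one holds for every rho below 1, but the size of the loss is illustrative. At 0.5 SD and 50 per arm, the 2-df gain runs from 28 points at rho 0.3 (0.57 to 0.85) through 16 at rho 0.5 to under one at rho 0.8.

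The model form adds to the SAP's power problem; it does not account for all of it, and adjustment would not by itself make 100 students enough. The precision gain also relies on T1 being unaffected by allocation. The protocol describes assignment before the laboratory visits and does not say whether participants know their workshop at T1. The change should be made, as it uses data the trial already collects.

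**What to change.** For the between-arm tests, specify one of two models per outcome:
- keep T1, T2 and T3 as outcomes but constrain the T1 mean to be equal in both arms; or
- model T2 and T3 only, with terms for T1 value, Group, Visit, Group x Visit and T1 value x Visit.

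The two are nearly, but not exactly, equivalent under dropout, because the constrained model keeps students who have T1 only.

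In place of the three-visit Group main effect, report the T1-adjusted YES+ versus WOW! difference at T2, at T3 and averaged over both. The visit-specific results are needed because the average can hide an effect that fades or grows. For cortisol and ECG, which have four recordings per visit, define the T1 value as the same summary or the same time point as the outcome. State whether participants knew their workshop at T1.

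The planned within-group changes and their Bonferroni factor of 4 can stay. The cost is SAP wording and one more model specification per outcome, with no new data.

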## 2) Purpose

Addressing the gap in the literature described above and to provide further preliminary data on the specific effects of YES+ on well-being and stress physiology, this study aims to evaluate measures of self-reported wellness across a variety of questionnaires, in addition to changes in heart rate variability and salivary cortisol levels with a stress induction task. To control for expectancy effects, overall time spent with the workshop, social contact, and exposure to cognitive stress management strategies that may influence the observed effects of YES+ not specific to the yogic breathing and deep social connectedness at the core of the YES+ targets, a comparison workshop with all of these potential supplementary contributors will be included, titled “Wisdom On Wellness” (WOW!).

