**8) Research procedures involved in the Human Research**

An overview of the study involvement is illustrated in Figure 1. Participation will include three laboratory visits at pre-workshop (T1), post-workshop (T2), and 1-2 month follow-up (T3) time points and four workshop sessions described below.

**Figure 1.** Overview of study timeline for each participant.

*Screening:* Interested participants will first be directed to an online pre-screening survey. The survey will begin with a prompt describing the study and requiring understanding via checkbox that the survey is for screening purposes. The survey will collect information such as name, e-mail address, date of birth, motivation for the study, student status, prior contemplative practice experience, ability to meet the time commitment, panic and bipolar symptoms, and potential affiliation with other

participants. If any of the exclusion criteria indicated above are met, the participant will be notified of ineligibility.

[figure not shown]
*Enrollment and randomization:* Eligible participants will be first grouped in clusters with any other participants with known affiliations stated in the online screener, in order to minimize possibility of learning about material of the other workshop, then assigned a workshop via random number generator.

*Laboratory Visits:* In-person laboratory visits will be conducted at the University of Arizona Respiratory Physiology Laboratory on the main UA campus. Workshops will be conducted in various buildings on the main UA campus depending on reservation availability.

Actigraphy, sleep diary, online questionnaires and practice logs measures will be completely remotely after the instruments are provided to participants during an in-laboratory visit.

In addition to actigraphy, sleep diary, online questionnaires, and home practice logs (for T2 and T3 time points) the following data will be collected during each laboratory visit: electrocardiography (ECG) with concurrent respiratory inductance plethysmography (RIP) and pulse oximetry recordings, as well as salivary cortisol at baseline, post-stress induction task, 30-min post-stress-induction-onset, and 45-min post. ECG, RIP belts, and pulse oximetry will be recorded continuously, in addition to the designated resting recording periods. An overview of the laboratory visit (identical across T1, T2 and T3) is provided in Figure 2.

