**WOW! workshop.** A comparison workshop titled “Wisdom On Wellness” (WOW!) will be implemented to control for potential expectancy effects, time commitment, group-based interactions, and wisdom/knowledge of YES+ that is anticipated to have beneficial effects on stress management and well-being, allowing for more rigorous evaluation of the contemplative practices and other activities unique to the YES+ workshop. The material used to guide interactions in WOW! will be similar to the material of YES+ and will be taught by a trained instructor with supervision by the Principal Investigator and Study Coordinator. This workshop differs from YES+ due to the increased focus on cognitive approaches to conceptualizing and managing stress (e.g. thoughts about the past and future versus present moment), and absence of physical or somatic activities. Using a focus group format, whereby the instructor primarily facilitates discussion, a variety of topics will be covered such as the nature of stress for humans, response to stressful events, time management, study skills, alcohol and drug use, personal values, career exploration, sleep habits, and nutrition.

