## 11) Potential benefits to subjects and/or society

*Benefit to participants is anticipated from both workshops in terms of stress-management tools and overall well-being, although some may benefit more than others in one workshop or the other. Participants may also benefit by contributing to scientific knowledge stress physiology and well-being in college students and other adults.*

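### The SAP makes each arm's own pre-post change the main analysis and specifies no YES+ minus WOW! estimate or confidence interval, although the randomised comparison is what addresses the trial's purpose.

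*SAP*

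**What the plan says.** The SAP's single analysis paragraph fits linear mixed models, and "results will be reported for main effects of Visit (pre, post, follow-up) and Group (YESplus, WOW), as well as Visit x Group interaction". It then says that, "due to limited statistical power of this sample to detect interactions, analysis will focus on within-group change from pre- to post-workshop", adds the change from pre-workshop to follow-up, and ties the effect size to those within-group changes. Multiplicity is handled by "multiplying uncorrected p values by 4 (the number of post-hoc comparisons per model"), and the text applies this correction to the within-group comparisons. Cohen's d is named, with no between-group version and no standardiser. No between-arm contrast, estimate or confidence interval is named, and the protocol has no statistical section that would supply one.

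The protocol gives the study a comparative aim. Section 3, 2) Purpose, seeks "further preliminary data on the specific effects of YES+ on well-being and stress physiology" and says why WOW! is included: "To control for expectancy effects, overall time spent with the workshop, social contact, and exposure to cognitive stress management strategies". The WOW! workshop description in 8) Research procedures adds that the comparator is there for "allowing for more rigorous evaluation of the contemplative practices and other activities unique to the YES+ workshop". Participants are randomised between the two workshops (8), Enrollment and randomization).

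**The concern.** A pre-to-post change within the YES+ arm combines any YES+-specific effect with expectancy, contact time and shared content, which WOW! was included to remove. It also contains calendar time, regression to the mean and the effect of repeating the stress visit: "An overview of the laboratory visit (identical across T1, T2 and T3) is provided in Figure 2". A concurrent randomised arm deals with all of these, but only if the arms are compared.

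The protocol expects both arms to improve (Section 3, 11) Potential benefits): "Benefit to participants is anticipated from both workshops in terms of stress-management tools and overall well-being". A significant change in YES+ is therefore expected even if nothing specific to YES+ works.

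The between-arm terms that remain do not fill the gap. The Visit x Group interaction is an omnibus test on 2 degrees of freedom; its p-value carries neither direction nor size. The Group main effect averages over all three visits, including pre-workshop. A lasting difference of d therefore appears as (0 + d + d)/3 = 2d/3, mixed with any baseline imbalance.

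The practical risk is that two columns of within-arm p-values get compared with each other. The SAP does not plan that reading, but it does not rule it out, and the correction by 4 does not protect it.

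**Working it through.** **1. The plan's own figure.** 2 arms x 2 changes (post minus pre, follow-up minus pre) = 4. The per-test level is 0.05/4 = 0.0125, and 4 x 0.0125 = 0.05. The multiplier reproduces, and the four within-arm comparisons use it up: none of the four is between arms.

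**2. Inputs.** Planned N is 100 (Protocol Section 3, 6) Study Population). The documents give no allocation ratio, analysed N, SD, effect size, visit correlation, dropout rate or clustering figure, and no power calculation. Assumptions: n = 50 per arm unless varied, two-sided tests, independent participants, equal correlation r between visits.

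**3. Error if significance in one arm only is read as a difference.** Let both arms truly change by the same standardised amount dz (mean change / SD of change). Let p be the power of a paired t-test at 0.0125 (noncentral t, n = 50). The chance that exactly one arm is significant at a given visit is 2p(1 - p). At dz = 0.3, p = 0.329 and 2 x 0.329 x 0.671 = 0.441.

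| dz | 0 | 0.2 | 0.3 | 0.4 | 0.5 | 0.6 | 0.8 |
|---|---|---|---|---|---|---|---|
| One visit | 2.5% | 23% | 44% | 48% | 29% | 10% | 0.3% |
| Either visit (simulated, r = 0.6) | 5% | – | 65% | 70% | 46% | 18% | 0.6% |

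The one-visit maximum is 50%, near dz 0.36, and the figure is at least 20% from about 0.19 to 0.54. Half of the one-visit cases favour YES+. With equal change in both arms, the interaction and the between-arm contrasts below keep their error at about 5%.

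**4. Power for a lasting between-arm difference d (in SD units of one visit).**

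- Interaction: noncentral F with lambda = (n/2)(2/3)d²/(1 - r), df 2 and 2(2n - 2). For d = 0.5, r = 0.6: 25 x 0.667 x 0.25/0.4 = 10.42, df 2 and 196, power 83%.
- One baseline-adjusted visit contrast at 0.025: SD = sqrt(1 - r²) = 0.80, SE = 0.80 x sqrt(2/50) = 0.16, noncentrality 0.5/0.16 = 3.13, df 97, power 80%.
- Baseline-adjusted mean of post and follow-up at 0.05: SD = sqrt((1 + r)/2 - r²) = 0.663, SE = 0.133, noncentrality 3.77, power 96%.
- At least one of the two visit contrasts at 0.025: simulated.

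| n per arm, d, r | Interaction | One visit contrast | At least one of two | Mean contrast |
|---|---|---|---|---|
| 50, 0.5, 0.6 | 83% | 80% | 93% | 96% |
| 50, 0.4, 0.6 | 63% | 59% | 77% | 85% |
| 50, 0.3, 0.6 | 39% | 35% | 52% | 61% |
| 40, 0.5, 0.6 | 73% | 69% | 85% | 91% |
| 30, 0.5, 0.6 | 59% | 55% | – | 82% |
| 20, 0.5, 0.6 | 42% | 37% | – | 64% |

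At n = 50, d = 0.5 and r = 0.3, interaction power is 57%. A single corrected visit contrast gains nothing over the interaction in these rows. The pair taken together, where computed, and the mean contrast do gain.

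**5. If the effect fades.** With 0.5 SD at post only (n = 50, r = 0.6), the mean contrast estimates 0.25 SD and its power falls to 46%. The corrected post contrast keeps 80% and the interaction 83%.

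**6. Precision.** At r = 0.6 and n = 50, the 95% CI half-width is 1.985 x 0.16 = 0.32 SD at one visit and 1.985 x 0.133 = 0.26 SD for the mean. A plain difference in change, without baseline adjustment, has half-width 0.397 change-score SD, or 0.397 x sqrt(2 x 0.4) = 0.36 SD.

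**7. Clustering.** Affiliated participants are randomised together and workshops are delivered in groups, which lowers these powers. As an illustration, an assumed ICC of 0.05 with groups of 12.5 gives a design effect of 1 + 11.5 x 0.05 = 1.575. The effective number is then 50/1.575 = 32 per arm, close to the 30-per-arm row.

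**The case against.** The best defence is that the randomised comparison is demoted but not dropped. The interaction is reported for every model, so a reader would see a valid between-arm test. The large error rates in step 3 describe a reading the SAP does not propose. Both arms' changes will be shown, so the sign and rough size of the difference could be worked out. All of this is correct. What is missing is a named contrast with its uncertainty, and a sentence closing off the invalid reading.

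A second argument is that the power worry may be well founded. The SAP postdates the protocol by about two years and speaks of this sample's limited power, so the analysed N may be well under 100. At 20 per arm, interaction power for 0.5 SD is 42%. This also stands, and the 83% should not be taken as the trial's actual power. But low power means the between-arm estimate will be imprecise, which is a reason to show it with its interval. It does not make within-arm change answer the comparative question.

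A third is that the study calls itself preliminary and its SAP title presents the effects of two workshops, so within-arm description is legitimate. It is, as description. The protocol nevertheless gives WOW! a control role, and a later trial would need the between-arm effect size and interval from preliminary data.

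**Conclusion.** The concern holds and should be fixed. Followed as written, the analysis on which the SAP concentrates does not estimate the YES+-specific effect that the protocol sets out to study, and nowhere is a YES+ minus WOW! estimate with a confidence interval specified. This does not depend on any assumed number; it follows from the text and from the multiplier of 4.

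The size of the consequence does depend on assumptions. With 50 per arm, reading one-arm-only significance as a difference would be wrong at a given visit in 23 to 48% of trials for equal true changes of 0.2 to 0.5 change-score SD. That figure is conditional on such a reading. For a lasting effect at r = 0.6, the mean contrast has more power than the interaction at every sample size shown, so the power argument does not support the within-arm focus. For an effect that fades by follow-up, the mean contrast is the weaker choice.

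**What to change.** Make the YES+ minus WOW! difference, adjusted for the pre-workshop value, the main result of each model, with estimate, 95% CI and p-value. The SAP's model has pre-workshop as a level of Visit, so the adjustment needs its own specification. One way is to use post and follow-up as outcomes with the pre-workshop value as covariate (and not also as an outcome). The other is a three-visit model in which the arms share a common pre-workshop mean. An unadjusted difference in change from the existing model would meet the core need, with a wider interval.

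State one of two options in the SAP before group-labelled results are examined:

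- **Option A.** The average over post and follow-up is the single main contrast at 0.05, with the two visit-specific differences and CIs as supporting results. This has most power if the effect lasts.
- **Option B.** The differences at post and at follow-up are two main contrasts, with p multiplied by 2. This protects against an effect that fades.

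The documents do not show whether group-labelled results had already been seen. If they had, the change should be labelled as made afterwards.

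Keep reporting the Visit x Group interaction. Report within-arm changes and their Cohen's d as descriptive, and add a between-arm standardised difference with its standardiser defined. Add a sentence such as: *No YES+-specific effect or superiority will be concluded from within-group significance, or from a difference in significance between arms.*

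The cost is SAP wording and a few lines of model syntax. Headline p-values will be less favourable than the within-arm ones, and Option A loses power if the effect does not last (46% against 80% for the corrected post contrast in the case above).

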## 6) Study Population

**100 college students** (50% female) will be recruited into the current study. Persons expressing interest in the study will be screened along several health dimensions and invited to participate in the proposed research according to the following criteria:

- a) 18-35 years of age. This age range is recommended for the YES+ workshop to capture qualitative consistencies in the unique challenges that face college students and optimize social connectedness during the workshop.
- b) Current identification with student status, which may include undergraduate, graduate, continuing studies, or post-baccalaureate/pre-doctoral.
- c) No history of panic disorder, psychosis, or mania (with or without psychotic features), which may be risk factors for adverse effects of the yogic breathing intervention. These symptoms will be pre-screened via online questionnaire. The use of psychoactive medication will be monitored via sleep diary.
- d) No current substance dependence, assessed via online self-report pre-screening questionnaire.
- e) No current use of medications with known effects on sleep or stress physiology including antidepressants (SSRI, SNSI, NDRI, atypical, TCA, MAOI), antipsychotics, benzodiazepines, non-benzodiazepine receptor agonists, melatonin and melatonin receptor agonists, orexin/hypocretin receptor antagonists, barbiturates, mood stabilizers, anticonvulsants, anticholinergics, first generation antihistamines, and stimulants including NRI, antihypertensives, opioids, or systemic (non-topical) corticosteroids.

In addition, a total of **4 workshop instructors** are expected to enroll in this study to provide questionnaire information regarding expectancy of workshop benefit for participants. All instructors must have prior training with the specific workshop to be led.

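### Multiplying all four within-group p values by 4 is valid, but Holm's step-down method keeps the same 5% limit and would add about 0 to 10 points of power per real effect

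*SAP*

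**What the plan says.** The statistical analysis paragraph of the SAP plans linear mixed models with post-hoc tests of "within-group change for YESplus and WOW at post and follow-up compared to pre-workshop". It makes these tests the focus of the analysis, in preference to the Visit x Group interaction, "due to limited statistical power of this sample to detect interactions".

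On multiplicity it states that "a Bonferroni correction will be applied by multiplying uncorrected p values by 4 (the number of post-hoc comparisons per model". The adjusted values are then held against the usual threshold, in its words "allowing alpha to remain at .05 for significance". The reason given is "to balance type I and type II error with these within-group comparisons". No step-down method is mentioned.

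Neither document gives a power calculation, a target effect size, a standard deviation, a correlation between visits or a dropout rate. On effect size the SAP says only that "Effect size estimates will be calculated with Cohen's d", which makes it an output. The Protocol (6, Study Population) plans for "100 college students". Under section 8 (Enrollment and randomization) participants are grouped by affiliation and "then assigned a workshop via random number generator", with no ratio stated.

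**The concern.** The SAP justifies its correction as a balance between the two types of error. Single-step Bonferroni holds every comparison to 0.05/4, however many of the others have already been rejected. Holm's method relaxes the threshold after each rejection and keeps the same familywise limit under any dependence. Measured against the SAP's own aim, the planned rule therefore accepts more type II error than its 5% limit demands, on the tests that carry the analysis. At stake is power for the second, third and fourth comparisons in each model, not the validity of any result.

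**Working it through.** **1. The plan's own figure.** 2 groups x 2 contrasts (post and follow-up, each against pre) = 4 comparisons, which matches the SAP. The per-comparison level is 0.05/4 = 0.0125. If the tests were independent and all nulls true, the familywise error would be 1 − (1 − 0.0125)^4 = 0.049, against 1 − (1 − 0.05)^4 = 0.186 with no correction. The multiplier is right.

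**2. What Holm changes.** Order the four p values. Compare the smallest with 0.05/4 = 0.0125, the next with 0.05/3 = 0.0167, then 0.05/2 = 0.025, then 0.05, and stop at the first failure. Two facts follow without simulation:
- No threshold is below 0.0125, so anything Bonferroni rejects, Holm rejects.
- The first step is the same in both, so the chance of at least one rejection among the four is identical.

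**3. Assumed inputs.** None of these is in the documents: two-sided tests; 1:1 allocation; 25 to 50 analysed per arm (100/2 = 50 is the ceiling if everyone recruited is analysed); dz of 0.3 to 0.5; correlation 0.5 between the two changes in an arm, which share the pre value; one to four of the changes real. Simple paired tests stand in for the mixed-model contrasts.

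**4. Check of one cell by formula.** With n = 50 and dz = 0.4, the noncentrality is 0.4 x √50 = 2.828. The two-sided critical value at 0.0125 is 2.498. Bonferroni power is Φ(2.828 − 2.498) = 63%.

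**5. Gain in average power per real effect, Holm minus Bonferroni, in percentage points** (normal approximation, 400,000 replicates; Bonferroni power in the third column):

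| n per arm | dz | Bonferroni | 4 real | 3 real | 2 real | 1 real |
|---|---|---|---|---|---|---|
| 50 | 0.3 | 35% | 6.3 | 3.5 | 1.8 | 0.1 |
| 50 | 0.4 | 63% | 10.2 | 5.5 | 2.3 | 0.1 |
| 50 | 0.5 | 85% | 7.4 | 4.3 | 1.7 | 0.1 |
| 35 | 0.3 | 24% | 3.7 | 2.1 | 1.2 | 0.1 |
| 35 | 0.4 | 45% | 8.1 | 4.5 | 2.1 | 0.1 |
| 35 | 0.5 | 68% | 10.1 | 5.6 | 2.3 | 0.1 |
| 25 | 0.3 | 16% | 2.1 | 1.2 | 0.8 | 0.1 |
| 25 | 0.4 | 31% | 5.4 | 3.0 | 1.6 | 0.1 |
| 25 | 0.5 | 50% | 9.0 | 4.9 | 2.2 | 0.1 |

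The two weakest settings are dz 0.3 with 25 or 35 per arm. With four real effects of equal size and Bonferroni power fixed in advance, the gain is 5.2 points at 30% power, 10.0 at 60% and 70%, and 5.6 at 90%.

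**6. Paired t tests instead of the normal approximation.** With 50 per arm and all four dz = 0.4, power per comparison goes from 60% to about 70%. With 35 per arm and all four dz = 0.5, the gain is 11 points. With 50 per arm, YESplus at 0.5 and WOW at 0.3, the WOW comparisons go from 33% to 46% and the YESplus ones from 82% to 87%. Equal effects are therefore not needed for a material gain.

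**7. Error.** With no true change anywhere, familywise error is 4.7% for both methods. With two real effects at dz 0.5 and 50 per arm, error on the two true nulls is about 2.4% with Bonferroni and 4.2% with Holm, still under 5%.

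**8. What Holm does not recover.** In the cell with n = 50, dz = 0.4 and all four real, an uncorrected test has 80.8% power, Bonferroni 63.0% and Holm 73.1%. Holm wins back (73.1 − 63.0)/(80.8 − 63.0) = 57% of the loss.

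**The case against.** The planned method is pre-specified, correctly counted, conservative and easy to report, so choosing Holm is a preference and no error is being corrected. That stands.

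The size of the gain depends on how many of the four changes are real. Section 11 of the Protocol anticipates benefit from both workshops, which makes four real changes plausible. But section 8 describes WOW as a comparison workshop controlling for expectancy, time and group contact, so real WOW changes at both visits on every outcome cannot be taken for granted. The analysed number may also fall below 50 per arm: section 13 foresees drop-outs, and section 15 allows removal for incomplete attendance. A reader might infer from the favourable scenarios that the plan forgoes about 10 points per comparison. The documents do not support that as a general figure.

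A reader might also infer that the SAP itself calls these within-group tests underpowered. It does not: its remark on power concerns interactions only.

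Nor is Holm free. The 5% bound is the same, but more of it is used when some effects are null: with YESplus at dz 0.5 and WOW null, the false-positive rate for each WOW comparison rises from about 1.2% to 2.4%. Bonferroni has simple matching intervals (at 98.75%); Holm has none equally simple, and a Bonferroni interval can include zero where Holm declares significance. These are real but small costs.

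**Conclusion.** The point holds as an optional gain in efficiency. That Holm keeps the 5% familywise limit under any dependence and never loses a rejection is certain and needs no assumption.

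The size is less certain. Over the assumed range it is about 0 to 10 points of average power per real effect, with a top of about 11 using t tests. Most of the gain comes when all four changes are real and Bonferroni power is moderate (about 50% to 80%). The figures rest on assumed effect sizes, correlation and analysed numbers, and on paired tests standing in for the mixed model.

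The documents do not support reading the planned correction as invalid. Nor does Holm bear on two separate matters: the reduced weight given to the between-group comparison, and multiplicity across the many outcome models.

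**What to change.** Before results are seen, replace the multiply-by-4 rule in the SAP with wording such as:

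*Within each model, the four within-group p values will be adjusted by Holm's step-down method (ordered from smallest to largest, multiplied by 4, 3, 2 and 1, each adjusted value no smaller than the one before it, capped at 1) and judged at .05.*

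Add a sentence saying which confidence intervals will be shown, unadjusted or Bonferroni, and that they may not agree with the Holm decision in every case.

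The cost is one or two sentences. No new data or software is needed, because the adjustment can be done in a spreadsheet from the SPSS p values. If results have already been examined, keep Bonferroni as the reported rule and show Holm only as a labelled supplement, since a later switch would look opportunistic.
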